| 
Study objectives
 | 
 ● To describe the characteristics of COVID-19 and its sequelae in several types of fragile populations. ● To describe the rate, the etiology (SARS-CoV-2 variants), the severity of COVID-19, and the rate of re-infections in several types of fragile patients. ● To evaluate the immunologic response to the COVID-19 vaccination in selected fragile populations. ● To evaluate the safety of COVID-19 vaccination in selected fragile populations. |

| | |
|--------------------|--|
| | 
 Identify human genetic markers and epigenetic characteristics in frail patients during post-vaccination monitoring and in case of breakthrough infections as well as to analyse the gut microbiome in such patients |
| Study population | Patients of all age and any comorbidity included in an ORCHESTRA fragile population cohort |
| Inclusion criteria | 
 Any age Any comorbidity Person (or attorney or deputy who has been authorized to make the decision for patients who lack capacity) consent to participate or appropriate local waiver of consent. |
| Exclusion criteria | Patients did not agree to participate. |
| Study design | 
Multicenter, multinational observational study aimed at building several types of fragile populations in which to assess the rate and the clinical spectrum of COVID-19, with particular interest in long-term follow-up, and at monitoring clinical and immunological response after SARS-CoV-2 vaccination in fragile subjects.
 
For long-term follow-up of fragile patients with COVID-19, a predefined schedule of assessment is planned in alignment with Work Package (WP) 2. Patients already diagnosed with COVID-19 can be included if baseline data according to WP2 protocol have been collected, and if follow-up visits are possible.
 
For assessing the clinical and immunological response to vaccination, patients will be prospectively evaluated at baseline (first and
 |

| | |
|--------------------|---|
| | second vaccination doses), and at multiple timepoints after vaccination with clinical and immunological assessments. |
| Vaccines | Approved COVID-19 vaccines |
| Follow-up | Patients will be followed-up for up to 18 months after the SARS-CoV-2 infection diagnosis or up to 12 months after vaccination. |

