3.2 Schedule of assessments (SoA)

Table 1. Schedule of assessments for long-term follow-up in COVID-19 patients.

| | COVID-19 (2 weeks ¹ ± 2 weeks) | 3 months ¹ (± 1 month) | 6 months ¹ (± 1 month) | 12 months ¹ (± 2 months) | 18 months ¹ (± 3 months) |
|--|---|--------------------------------------|--------------------------------------|--|--|
| Screening/baseline | | | | | |
| Inclusion criteria ¹ | X | | | | |
| Demographics ² | X | | | | |
| Healthcare setting ³ | X | | | | |
| Length of hospital stay, days | X | | | | |
| ICU admission | X | | | | |
| Medical history ⁴ | X | | | | |
| Treatment | | | | | |
| Comorbidity management ⁵ | X | X | X | X | X |
| Anti-COVID therapy ⁶ | X | | | | |
| Antibiotic therapy | X | X | X | X | X |
| Oxygen therapy ⁷ | X | X* | X* | X* | X* |
| SARS-CoV ² ⁸ and other respiratory pathogen vaccination ⁹ | X | X | X | X | X |
| Clinical assessment | | | | | |
| Relevant medical new events ¹⁰ | X | X | X | X | X |
| COVID-19 symptom ¹¹ onset | X | | | | |
| COVID-19 symptom end | X | X* | X* | X* | X* |
| COVID severity ¹² | X | | | | |
| SOFA score | X | | | | |
| Vital signs ¹³ | X | X | X | X | X |
| Physical examination ¹⁴ | X | X | X | X | X |
| 12-lead electrocardiography | X | X | X | X | X |
| 6-minute walking test | X | X | X | X | X |
| DLCO (diffusing capacity for carbon monoxide) | X | X | X | X | X |
| Pulmonary function test ¹⁵ | X | X | X | X | X |
| Questionnaires | | | | | |
| Functional status ¹⁶ | X | X | X | X | X |
| Respiratory impairment ¹⁷ | X | X | X | X | X |
| Mental health ¹⁸ | X | X | X | X | X |
| Risk perception and behaviour^{19, 20} | | | | | |
| SARS-CoV-2 vaccination: acceptance/non-acceptance and reasons ²¹ | | X | | X | X |
| Socio-economic indicators | | X | | X | X |
| Use of resources (COVID-19 unrelated) | | X | | X | X |
| Imaging | | | | | |
| Lung ultrasound | X | X | X* | X | X* |
| X-ray | X | X | X* | X* | X* |
| High-resolution CT scan | X | X | X* | X* | X* |
| Cardiac ultrasound | X | X | X* | X | X* |
| Cardiac MRI ²² | X ²¹ | X ²¹ | X* | X ²¹ | X* |
| Biochemistry | | | | | |

| | | | | | |
|---|---|-------------------|-------------------|-------------------|----|
| Blood tests ²³ | X | X | X* | X | X* |
| Arterial blood gas test (pO ₂ /pCO ₂ /pH) | X | X | X* | X* | X* |
| Urine tests ²⁴ | X | X | X* | X | X* |
| Immunology | | | | | |
| Immune - serology and type I IFNs autoantibodies | X | X | X | X | X |

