| Immune - cytokine and chemokine | X | X ³⁵ | X ³⁵ | X ³⁵ | X* |
| Immune - cellular | X | X ³⁵ | X ³⁵ | X ³⁵ | X* |
| Microbiological tests-NP swabs | | | | | |
| Viral variant and metagenomics sequencing | X | X*, ³⁴ | X*, ³⁴ | X*, ³⁴ | X* |
| EDTA whole blood | | | | | |
| Genetic and epigenetic analysis | X | X | X | X | X |
| Stool Sample (faeces or rectal swab) | | | | | |
| Metagenomic sequencing | X | | X | | X |
| Microbiological tests | | | | | |
| SARS-CoV-2 molecular test in nasopharyngeal swab or tracheal aspirate or bronchoalveolar lavage or saliva | X | X* | X* | X* | X* |
| Adjunctive variables for specific fragile populations | | | | | |
| HIV | | | | | |
| HIV-infection status ²⁵ | X | X | X | X | X |
| HIV-Infection therapy ²⁶ | X | X | X | X | X |
| Assessment of adherence to follow-up visits and antiretroviral therapy | X | X | X | X | X |
| Elderly | | | | | |
| Cognitive status ²⁷ | X | X | X | X | X |
| Pregnant women/new born | | | | | |
| History of positive SARS-CoV-2 molecular test on amniotic fluid or breast milk ²⁸ | X | | | | |
| History of detection of microthrombotic disease on placenta tissue or umbelical cord tissue | X | | | | |
| Children | | | | | |
| History of positive SARS-CoV-2 molecular test on amniotic fluid or breast milk ²⁹ | X | | | | |
| Biometric paramethers ³⁰ | X | X | X | X | X |
| Transplant | | | | | |
| Transplant general information ³¹ | X | | | | |
| Graft function ³² | X | X | X | X | X |
| Immunosuppressive regimen ³³ | X | X | X | X | X |

| Onco-haematology | | | | | |
|---|---|---|---|---|---|
| Assessment of adherence to oncologic follow-up visits and therapy | X | X | X | X | X |
| Assessment of progression of the disease and relapse | X | X | X | X | X |
| Assessment of adverse events ³⁴ | X | X | X | X | X |

Footnotes

Modular data capture according to level of commitment (level I, level II, level III).

| | |
|-----------------|--|
| Level I | Assessments in level I are mandatory |
| Level II | Customized according to the feasibility of each cohort |

* Reassessed only if outside the normal ranges at the previous assessment or if clinically indicated

1. Day 0: first positive SARS-CoV-2 test

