7. OBJECTIVES

The primary objective of the ORCHESTRA fragile cohorts is to provide an extensive and harmonized collection of epidemiological and clinical data, and biological samples, to assess several features of COVID-19 in each cohort of fragile patients. These include:

- To assess the prevalence of SARS-CoV2 infection and COVID-19 disease in fragile patients;
- To describe the clinical spectrum of COVID-19 disease in different types of fragile patients;
- To analyze epidemiological, clinical and biological predictors of SARS-CoV-2 infection and prognosis in several types of fragile patients;
- To investigate the therapeutic management of COVID-19 and /or of the underlying condition and its impact on the outcome in fragile patients;

- To describe safety and efficacy of COVID-19 vaccination in selected cohorts of fragile patients;
- To describe the relationship between risk perception and adherence to preventive measures over time, including vaccine acceptance;
- To analyze the impact of COVID-19 pandemic on the use of health care services;
- To analyze the socio-economic determinants of infection and disease severity, and the socio-economic impact of the pandemic on cohort specific socio-economic indicators;
- To investigate the psychological consequences of lockdown in fragile patients.
- Identify human genetic markers and epigenetic characteristics in frail patients during post-vaccination monitoring and in the onset of breakthrough infections as well as to analyse the gut microbiome in such patients

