8. STUDY DESIGN

This is an observational retrospective and prospective longitudinal cohort study of several types of fragile patients (see details below). All ages and comorbidities will be included. All the cohorts will be mixed, including patients with and without past or new diagnosis of SARS-CoV2 infection (COVID-19 positive and COVID-19 negative groups) during the study period.

Study will start soon after the approval by the Ethics Committee and will end in June 2023. For the baseline characteristics and past COVID-19 diagnosis, data will be recorded from February 2020. For the prospective part, patients will be recruited until June 2022. Minimum follow-up duration will be of: i) 12 months from the first vaccination dose for fragile patients who will receive anti-COVID-19 vaccination; ii) 18 months from diagnosis of SARS-CoV-2 infection for COVID-19 positive group, allowing a partial follow-up for participants whose SARS-COV-2 infection occur after January 2022; and iii) up to the end of recruitment for the other fragile patients (see Figure 1).

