For patients with a past and/or new diagnosis of SARS-CoV2 infection/COVID-19 disease a pre-established long-term follow-up including multiple diagnostic levels in order to adapt to all the participating cohorts is requested. A detailed overview of the schedule of the study visits and the clinical parameters to be recorded is shown in **Table 1**. Patients who have already had COVID, and new patients being diagnosed with COVID, who can be followed up to at least 12 months, and for whom data can be collected according to **Table 1** should be included. In specific fragile cohorts, such as children cohorts, virtual assessments are allowed.

For patients who have been or will be vaccinated against COVID-19 during the study period, a pre-established monitoring of safety and efficacy in terms of immunological response will be performed. A detailed overview of the schedule of the clinical and laboratory parameters to be recorded is shown in **Table 2**. Patients who have already been vaccinated, or will be vaccinated, who can be followed for 12 months, and for whom data can be collected according to Table 2 should be included. The monitoring should start from the days of first and second dose administration when possible (i.e. vaccination administered in the same center where the patient is followed for the fragile condition), alternatively patients will be monitored at 3±1, 6±2 and 12±3 months after the first vaccination dose.

- Vaccination safety will be assessed by a dedicated questionnaire (Annex 3) distributed to patients at baseline or during the first monitoring visit.

- Vaccination efficacy will be established analyzing the immune response at the predefined time-points. The humoral immune response to vaccination will be assessed by a serological assay able to detect anti-Spike and anti-Nucleocapsid antibodies as well as seroneutralization assays in sera samples. The latter will be useful to exclude possible natural infection at the baseline (1st/2nd dose, or first post-vaccination monitoring visit). The cytokine and cell-mediated immune response to vaccination will be assessed in a subgroup of patients by centralizing samples to a referral laboratory, according to local ethic rules and budget. The number of SARS-CoV-2 paucisymptomatic or symptomatic infection despite vaccination will be also assessed by SARS-CoV-2 detection in respiratory/saliva sample.

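### The follow-up condition for COVID-19 cases does not say what it admits them to; if sites apply it at entry, early deaths drop out of mortality, severity and prognosis

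*Protocol*

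**What the plan says.** The Study design row of the synopsis states: "Patients already diagnosed with COVID-19 can be included if baseline data according to WP2 protocol have been collected, and if follow-up visits are possible". Section 11 extends a condition of this kind to past and new cases: "Patients who have already had COVID, and new patients being diagnosed with COVID, who can be followed up to at least 12 months", with data obtainable according to Table 1, should be included.

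Both sentences stand in paragraphs about long-term follow-up, and Table 1 carries that title: "Table 1. Schedule of assessments for long-term follow-up in COVID-19 patients". Its clock starts at "Day 0: first positive SARS-CoV-2 test". The synopsis counts follow-up from diagnosis: "Patients will be followed-up for up to 18 months after the SARS-CoV-2 infection diagnosis". Section 8 reaches back in time: "For the baseline characteristics and past COVID-19 diagnosis, data will be recorded from February 2020". Section 14.8 puts the study start at about April 2021. The only stated relaxation of follow-up length is in Section 8, "allowing a partial follow-up for participants whose SARS-COV-2 infection occur after January 2022".

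Other sections are more open:
- Section 10 names missing consent as the sole exclusion and accepts a local waiver.
- Section 14.3 gives records-only data as an example for a waiver.
- Section 14.4 foresees retrospective data collection once a case is complete, including after death.

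The endpoints at stake are all-cause mortality and WHO severity (Section 12), the objective "To analyze epidemiological, clinical and biological predictors of SARS-CoV-2 infection and prognosis in several types of fragile patients" (Section 7), and the Cox and Fine-Gray models (Section 13).

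**The concern.** A condition that a patient can still attend visits, or can be followed for at least 12 months, cannot be met by someone who has died. For sequelae analyses this is unavoidable. For mortality, severity and prognosis counted from the first positive test, it selects survivors: deaths between diagnosis and enrolment disappear, severe cases are thinned out, and predictors that act through early death look weaker than they are. For new cases, an investigator who expects early death could judge that the condition is not met.

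Table 1 makes the ambiguity matter. It carries the rows for inclusion criteria, ICU admission, COVID severity and SOFA score, and its vital-signs note includes dead or alive. No other schedule shown collects these for COVID-19 cases. Even if the condition governs Table 1 alone, the protocol does not say how they are obtained for a case outside it. Section 9 lists 29 cohorts; if they read the sentences differently, their mortality figures are not comparable.

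**Working it through.** **Text, side by side.** The synopsis and Section 11 set a follow-up condition; Section 10 sets none. Sections 14.3 and 14.4 leave room for a record-based route, but Section 14.4 may mean only late data entry for patients enrolled while alive. Section 11 also finds past disease by interview, serology and swab or saliva specimens at scheduled visits, which cannot identify someone who has already died. Cohorts that registered cases at hospital attendance or admission (Sections 9.8.2 to 9.8.4) may be less exposed.

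**Gap.** February 2020 to April 2021 is 14 months, so at study start the earliest past cases would have had to survive about that long to enter.

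**Size.** The plan gives no figure to reproduce, and the documents do not supply the inputs. All inputs below are assumptions that show the mechanism. New cases are taken as fully captured.

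Inputs: 30-day mortality e = 1%, 10% or 20%; later hazard h = 0.5% per month; past cases enter alive at month m; s = share of all infected patients who are past cases.

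- True 18-month mortality: T = 1 − (1 − e)(1 − h)^17 = 9.1%, 17.4%, 26.5%.
- Alive at entry: S = (1 − e)(1 − h)^(m−1).
- Later risk: P = 1 − (1 − h)^(18−m) = 7.2% (m = 3), 5.8% (m = 6), 3.0% (m = 12).
- Observed = [s·S·P + (1 − s)·T] / [s·S + (1 − s)].

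| Past-case share, entry month | e = 1% | e = 10% | e = 20% |
|---|---|---|---|
| True | 9.1% | 17.4% | 26.5% |
| s = 25%, m = 6 | 8.3% | 14.7% | 22.3% |
| s = 50%, m = 3 | 8.2% | 12.6% | 18.0% |
| s = 50%, m = 6 | 7.5% | 12.0% | 17.5% |
| s = 50%, m = 12 | 6.1% | 10.7% | 16.4% |
| s = 100%, m = 6 | 5.8% | 5.8% | 5.8% |

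At m = 6, mortality is understated 1.1- to 1.2-fold with s = 25% and 1.2- to 1.5-fold with s = 50%. Among past cases alone, early mortality leaves no trace.

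**Predictor of early death.** Let it raise 30-day mortality from 5% to 15% with no later effect. The true 18-month risks are 12.8% and 21.9%, a ratio of 1.72. At m = 6 the observed ratio is 1.66, 1.55 and 1.00 for s = 25%, 50% and 100%. Over m = 3 to 12 it is 1.64 to 1.71 (s = 25%) and 1.51 to 1.66 (s = 50%).

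**Severity.** This is a separate scenario. Assume a mild/moderate/severe/critical mix of 60/20/12/8% and early deaths of 0/2/15/40% (5.4% overall). Severe plus critical is truly 20.0%. With all cases past it is (10.2 + 4.8)/94.6 = 15.9%; with s = 25% and 50% it is 19.0% and 18.0%.

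**Time at risk.** If survivors' time is counted from Day 0 without delayed entry, the months before entry, in which they could not die, enter the denominator. At m = 6 the hazard is 0.0584/(6 + 11.68) = 0.33% per month in place of 0.50%; it is 0.41% at m = 3 and 0.17% at m = 12.

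**The case against.** The strongest reply is that these are module conditions. Each sentence stands in a long-term follow-up paragraph, Section 11 ties its sentence to Table 1, and the next paragraph uses the same form for vaccinated patients and Table 2. Eligibility belongs to Section 10, which has no such condition, and Section 11 opens with patients already included. The design is partly retrospective, collection after death is foreseen, and Table 1 has a vital-status field in its acute column. Section 9 says that 10,300 of about 19,784 subjects are already registered and on active follow-up, so some deaths may be known without later enrolment, although no registration dates are given.

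Most of this stands. The module reading is the more natural one. A reader might infer that the protocol bars deceased cases, or that its mortality results will be understated; the documents do not support either. Nor do they support limiting the point to past cases, because the Section 11 sentence covers new ones too.

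What the reply does not supply is a sentence saying that cases failing the condition still count, or that Section 14.4 covers patients never enrolled alive. Figure 1 and one item of the Section 10 list are not shown, so this absence is established only for the text at hand. Delayed entry could be left to an analysis plan, but no plan can recover records that sites were never told to abstract.

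**Conclusion.** The point holds as an ambiguity with consequences. The protocol conditions inclusion on possible follow-up, does not say included in what, and does not reconcile this with Sections 10, 14.3 and 14.4. Applied at entry, the wording understates mortality and severity, attenuates predictors of early death, and may do so unevenly across cohorts. Whether this happens depends on how sites read it. The true size cannot be derived from the documents: the figures above rest wholly on assumed mortality, entry month, past-case share and severity mix. It should be fixed, with moderate confidence, because the loss cannot be repaired once abstraction is over.

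**What to change.** 1. In the synopsis and Section 11, state that the follow-up condition governs only the Table 1 long-term follow-up (sequelae) analyses, for past and new cases alike.
2. State that SARS-CoV-2-positive patients enter the mortality, severity and prognosis analyses regardless of vital status or expected follow-up, with deceased past cases taken from existing cohort records where a local waiver allows.
3. In Section 14.4, state whether collection after death covers patients never enrolled alive.
4. Where only survivors can be enrolled, use the enrolment date as delayed entry in the Cox and competing-risk models, and report no cumulative mortality or severity distribution from those patients. For consented patients, the dated consent form (Section 14.3) gives that date.

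The cost is a few sentences and some record abstraction where a waiver exists. Precision early in follow-up falls where delayed entry is used, and early mortality will be available only from cohorts with a waiver.

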| Metagenomic sequencing | X | | X | | |
| Questionnaires¹ | | | | | |
| Risk perception and behavior | X ¹ | | | X | X |
| Socio-economic indicators | X ¹ | | | X | X |
| Use of resources (COVID-19 unrelated) | X ¹ | | | X | X |
| Adverse Events dedicated questionnaire | | X | X | X | X |
| Immune response | | | | | |
| Quantitative Ab anti-S IgG ⁵ | X | X | X | X | X |
| Qualitative Ab anti-N IgM+IgG ⁵ | X | | | | |
| Anti-SARS-CoV-2 sero-neutralization | X | X | X | X | X |
| Cytokine / chemokines | X | X | X | X | X |
| Anti-SARS-CoV-2 cell immunity | | X | | X ⁶ | X ⁶ |

Footnotes

Modular data capture according to level of commitment (level I, level II).

| | |
|----------|---|
| Level I | Assessments in level I are core and should be prioritized |
| Level II | Customized according to the feasibility of each cohort |

*3, 6 and 12 months counted from the 1st dose.

¹For centers able to follow patients since the administration of the first and second vaccination doses the baseline information and the risk perception behavior should be collected at one of these time-points, in the other cases such information should be collected during the first post-vaccination follow-up.

²The assessment at 2nd dose is mandatory in patients who will receive such dose within 8-12 weeks after first dose (current AstraZeneca vaccination schedule).

³If COVID-19 diagnosis, assessments reported in Table 1 are required.

⁴Relevant new medical events or worsening of previous conditions, including new malignancies (type of cancer, overall stage, Kaposi skin-visceral, Lymphoma localization-type, Leukemia lymphoid-myeloid acute-chronic), deep venous thrombosis, pulmonary embolism, infections (including a new SARS-CoV-2-infection during follow-up)

⁵At least one time-point at 1st and 2nd dose is required.

⁶At least one of the three timepoints (month 3, month 6, month 12) is required.

⁷At least one of the four timepoints (2nd dose, month 3, month 6, month 12) is required.

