ANNEX 3 – Questionnaire for monitoring of adverse events to COVID-19 vaccination

A) Demographics – Anamnesis

Age: _____

Sex: M F

Special population: HIV Cancer Solid organ transplant Haematological stem cell transplant

If solid organ transplant, please specify: Liver Kidney Heart Lung

Drug/food allergies: Y N If yes, please specify: _____

Previous serious adverse events to vaccination: Y N

Underlying diseases:

Renal Cardiovascular Asthma Diabetes mellitus Anaemia/Blood disorders

Seizure/Epilepsy

Other nervous system disease: Y N If yes, please specify: _____

Concomitant medications: _____

Blood transfusion in the last year: Y N

Treatment with immunoglobulin or antivirals in the last year: Y N

Other relevant conditions: _____

B) Adverse event report

First dose (dd/mm/yy): _____

Second dose (dd/mm/yy): _____

Clinical events after the first dose: Y N

Clinical events after the first dose: Y N

Headache: Y N

Asthenia: Y N

Fever ($\geq 38^{\circ}\text{C}$): Y N

Nausea: Y N

Vomiting: Y N

Lymphadenopathy: Y N

Tachycardia: Y N

Flushing: Y N

Syncope: Y N

Pruritus, erythema or pain in injection site: Y N

- Generalised urticaria: Y N
- Serious allergic events (anaphylaxis, angioedema): Y N
- COVID infection after vaccination: Y N
- Use of paracetamol or non-steroidal anti-inflammatory drugs: Y N
- Requirement for use of other drugs: Y N If Yes, please specify: _____
- Demyelinating disorders: Y N
- Encephalitis/Encephalopathy: Y N
- Peripheral neuropathy: Y N
- Muscular weakness and/or paralysis: Y N
- Visual impairment (including optic neuritis): Y N
- Walking disturbance: Y N
- Blood disorders (anaemia, thrombocytopenia, leukopenia): Y N
- Seizures/Epilepsy: Y N
- Weakness and/or paralysis of facial muscle: Y N
- Vasculitis: Y N
- Renal disorders: Y N
- Liver function disorders: Y N
- Cardiac disorders: Y N
- Other adverse events: Y N If Yes, please specify: _____

[figure not shown]
If yes (complete for each reported event): day of onset (dd/mm/yy): _____

hospitalization/emergency department admission/general practitioner visit: Y N

Description of the event (laboratory data/administered drugs/other relevant information):

Recovery: Y N

ANNEX 4 – WP6 Deliverable 6.1_Mapping of retrospective samples and development of standardized protocols for prospective sampling

WP6 Deliverable 6.1

Mapping of retrospective samples and development of
standardised protocols for prospective sampling

UANTWERPEN

Project Classification

| | |

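### Annex 3 prints the first-dose event line twice with no second-dose line, and Section 11 states no repeat of a safety form that Table 2 schedules at four visits

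*Protocol*

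**What the plan says.** **Section 11 (Study procedures).** The vaccination safety bullet reads: "Vaccination safety will be assessed by a dedicated questionnaire (Annex 3) distributed to patients at baseline or during the first monitoring visit". It gives no later occasion. The paragraph before it refers to Table 2 for the schedule and says that vaccinated patients "for whom data can be collected according to Table 2 should be included". For centres that do not follow the dosing days, "alternatively patients will be monitored at 3±1, 6±2 and 12±3 months after the first vaccination dose". The efficacy bullet that follows explains baseline as either dose or the first monitoring visit after vaccination. The synopsis also ties baseline to the first and "second vaccination doses), and at multiple timepoints after vaccination with clinical and immunological assessments".

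**Table 2 (Section 3.2).** The row "Adverse Events dedicated questionnaire" is blank at the 1st dose and marked at the 2nd dose and at months 3, 6 and 12.

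**Annex 3, part B.** The form has a date field for the first dose and one for the second ("Second dose (dd/mm/yy"). Next come two identical lines, each reading "Clinical events after the first dose: Y N". No line asks about events after the second dose. A single list of Y/N items follows, and then, for each event, "If yes (complete for each reported event): day of onset (dd/mm/yy".

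**The concern.** Describing vaccine safety is a stated objective (synopsis and Section 7), and Annex 3 is the only instrument that Section 11 names for it. Two things weaken it.

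First, the duplicated line leaves the form without a direct question on events after dose 2. It is most likely a misprint for the second dose. As printed, only the onset date links an event to a dose.

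Second, the Section 11 sentence and Table 2 do not give the same collection schedule. Section 11 states repetition where it wants it: the socio-economic questionnaire is given at two time-points, and efficacy is assessed at predefined time-points. The safety bullet names one occasion and stops, so a site could reasonably take it as a single hand-out. Section 9 counts 29 cohorts in 14 countries. If some give the form once and others follow Table 2, differences in reported reactions between fragile populations would partly reflect how often patients were asked.

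**Working it through.** The protocol gives no figure to reproduce here. The check sets the texts side by side, counts form lines and table cells, and compares visit windows with the timing of the second dose.

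**1. Annex 3 part B, line count**

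| Element | Dose 1 | Dose 2 |
|---|---|---|
| Date field | 1 | 1 |
| Event Y/N line | 2 (identical) | 0 |

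From headache to other adverse events there are 29 Y/N items. None carries a dose label in the text available.

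**2. When the form is collected**

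| Occasion | Section 11 safety bullet | Table 2 |
|---|---|---|
| 1st dose | possible (baseline covers either dose) | blank |
| 2nd dose | possible | marked |
| Month 3 | possible (first monitoring visit) | marked |
| Month 6 | not mentioned | marked |
| Month 12 | not mentioned | marked |

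Table 2 gives 4 forms where the centre follows dosing, and 3 where monitoring starts at month 3. Section 11 names one occasion. The two agree that the 2nd dose or month 3 can be the first occasion. They differ on the 1st dose and on the repeats.

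**3. What a single hand-out could miss**

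Inputs: the Table 2 windows of 3 ± 1, 6 ± 2 and 12 ± 3 months, counted from the 1st dose; the second-dose interval of 8–12 weeks in Table 2 footnote 2; and one month = 365.25/12 = 30.44 days.

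- Second dose at 8–12 weeks: 8 × 7 = day 56 to 12 × 7 = day 84.
- Month 3 window opens: (3 − 1) × 30.44 = 60.9, about day 61.
- Month 6 window opens: (6 − 2) × 30.44 = 121.8, about day 122.
- Month 12 window opens: (12 − 3) × 30.44 = 274.0, about day 274.

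For each occasion that Section 11 permits:

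- *At the 1st dose:* no later reaction to either dose can yet be reported.
- *At the 2nd dose:* dose-1 events, and at most immediate dose-2 events.
- *At the first monitoring visit:* a month 3 visit from day 61 can come before a second dose given as late as day 84. If the second dose was given before day 61, this visit always follows it.

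The month 6 and month 12 forms always follow a second dose given by week 12 (84 < 122 < 274). They are 2 of the 4 scheduled forms, or 2 of 3 where monitoring starts at month 3, and they are the ones the Section 11 bullet leaves out.

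**The case against.** The strongest reply is that the system works if read as a whole.

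- **Repeats.** Section 11 sends the reader to Table 2, requires data collected according to it, and never restricts the form to one use. This stands: a site that follows Table 2 loses nothing through the Section 11 wording. A reader might infer that the protocol limits safety collection to a single hand-out, but the documents do not say so.
- **First occasion.** Baseline in Section 11 covers the 2nd dose as well as the 1st, and month 3 is also marked in Table 2. This stands in part: only the blank 1st-dose cell conflicts.
- **Attribution to a dose.** Annex 3 asks for both dose dates and an onset date per event, and Section 14.5 provides for queries on missing data. A reader might infer that dose-2 events go unrecorded or cannot be assigned. That does not follow: dated events can be assigned, and a form with every item answered no does report no events. What remains is the absence of a direct dose-2 question and full reliance on the onset date.
- **Parallel capture.** Table 2 also collects relevant new medical events at all five columns, and its footnote is open-ended. It may pick up serious events. It is not a reaction checklist, so the exposure is mainly in the reactogenicity items.
- **Limits of the text.** A figure is missing next to the onset line in Annex 3, so it cannot be claimed that the printed form lacks a completion date or any dose label. Table 2 also allows Level II items to vary by cohort, and the text does not show the level of this row. If it is Level II, some variation between cohorts is already accepted.

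**Conclusion.** The point holds in a limited form and should be fixed. Annex 3 has two event lines for dose 1 and none for dose 2, so attribution depends on the onset date. Section 11 names one occasion against four in Table 2. The conflict concerns the repeats and the 1st dose; the 2nd dose and month 3 can be reconciled.

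The loss is conditional on a site reading Section 11 as a single hand-out. That hand-out could then come before dose-2 reactions, and reaction items would be under-ascertained and differ between cohorts. The documents give no basis for estimating how many sites would read it so, and no number of lost events is claimed. The day counts assume a second dose at 8–12 weeks; with a second dose before about day 61, the month 3 form would always follow it.

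**What to change.** 1. Check the printed Annex 3 first, because a figure is missing from the text available.
2. In Annex 3 part B, change the second of the two identical lines so that it asks about clinical events after the second dose.
3. Make the onset date, which is already requested for each reported event, a required field in the form and the eCRF.
4. Reword the Section 11 safety bullet so that the form is collected at the Table 2 visits: the 2nd dose where the centre follows dosing, and months 3, 6 and 12.

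A dose tick per event and a completion date would help but are optional.

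The cost is one corrected line, one field setting and one reworded sentence. All the visits are already in Table 2, so none is added.
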